#### C.5.1.3 Major Adverse Cardiovascular and Cerebrovascular Events

Major adverse cardiovascular and cerebrovascular events (MACCE) is defined as a composite of:

- All-cause death
- Myocardial infarction (MI)
- All stroke, and

- Reintervention (defined as any cardiac surgery or percutaneous reintervention catheter procedure that repairs, otherwise alters or adjusts, or replaces a previously implanted valve)

#### C.5.1.4 Major Adverse Event

Major adverse event (MAE) includes:

- MACCE
- Acute kidney Injury
- Cardiac tamponade
- Prosthetic valve dysfunction
- Cardiogenic shock
- Prosthetic valve endocarditis
- Life-threatening, disabling or major bleeding
- Major vascular complication
- Cardiac perforation
- Valve malpositioning

#### C.5.1.5 Adverse Device Effect (ADE) or Device-Related Adverse Event

An ADE is an adverse event related to the use of an investigational medical device. During this clinical investigation an event should be considered related to the device when it is the result of the Medtronic CoreValve™ System (MCS) System:

- The transcatheter aortic valve (TAV)
- The delivery catheter system (DCS)
- The compression loading system (CLS/LS)
- The implant procedure

An event should be considered not related to the device when it is the result of:

- A pre-existing medical condition
- A new illness, injury or condition
- Medication

NOTE 1: This definition includes adverse events resulting from insufficient or inadequate instructions for use deployment, implantation, installation, or operation, or any malfunction of the investigational medical device.

NOTE 2: This definition includes any event resulting from use error or from intentional misuse of the investigational medical device.

#### C.5.1.6 Serious Adverse Device Effects (SADEs)

Adverse device effect that has resulted in any of the consequences characteristic of a Serious Adverse Event.

#### C.5.1.7 Unanticipated Adverse Device Effect (UADE)

An unanticipated adverse device effect or UADE is defined as “any serious adverse effect on health or safety or any life-threatening problem or death caused by, or associated with, a device, if that effect, problem, or death was not previously identified in nature, severity, or degree of incidence in the protocol or application (including a supplementary plan or application), or any other unanticipated serious problem associated with the device that relates to the rights, safety, or welfare of subjects” [21 CFR 812.3 (s)].

Those known adverse events related to the device, procedure or therapy are listed in Section O and in the Risk/Benefit Analysis section (Section D) of this document.

#### C.5.1.8 Unanticipated Serious Adverse Device Effect (USADE)

Serious adverse device effect which by its nature, incidence, severity or outcome has not been identified in the current version of the risk analysis report.

NOTE: Anticipated serious adverse device effect (ASADE) is an effect, which by its nature, incidence, severity or outcome has been identified in the risk analysis report.

#### C.5.1.9 Device Deficiency

Inadequacy of a medical device with respect to its identity, quality, durability, reliability, safety or performance.

NOTE: Device deficiencies include malfunctions, use errors, and inadequate labeling.

#### C.5.1.10 Technical Observation

A technical observation is a defect, malfunction, or failure of any part of the TAV or its components. This may pertain to the device or system not functioning according to its design intent. Each technical observation (whether or not associated with any untoward medical occurrence in a subject) will be reported on the Adverse Event (AE) eCRF and tabulated as an AE.

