#### C.5.1.1 Adverse Event

An adverse event (AE) is any untoward medical occurrence, unintended disease or injury, or untoward clinical signs (including abnormal laboratory findings) in subjects, users or other persons, whether or not related to the investigational medical device.

NOTE 1: This definition includes events related to the investigational medical device or the comparator.

NOTE 2: This definition includes events related to the procedures involved.

NOTE 3: For users or other persons, this definition is restricted to events related to investigational medical devices.

The following events in **Table 4** are expected to occur with any surgical implant and therefore should not be reported as AEs, unless they occur outside of the stated timeframe:

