#### C.5.2.4 Device Deficiencies and Technical Observations

Device Deficiency information and Technical Observations will be collected throughout the trial and reported to Medtronic.

Device Deficiencies and Technical Observations should be reported on an Adverse Event eCRF.

Device deficiencies that did not lead to an Adverse Event but could have led to an SADE:

- a) if either suitable action had not been taken,
- b) if intervention had not been made, or
- c) if circumstances had been less fortunate,

require immediate reporting (see **Table 6**). Initial reporting may be done on the eCRF completing as much information as is available. The original completed eCRF must be submitted to Medtronic as soon as possible.

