### TECHNICAL OBSERVATION

A defect, malfunction, or failure of any part of the Medtronic CoreValve™ System. This may pertain to the device or delivery and/or loading system not functioning according to its design intent.

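### Technical observations, a category defined only for the CoreValve system, are to be counted as adverse events even without patient harm, so any all-AE tabulation that follows this rule could be inflated for TAVI only

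*Combined protocol and SAP*

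**What the plan says.** C.5.1.10 sets the scope: "A technical observation is a defect, malfunction, or failure of any part of the TAV or its components". The definitions in O.2 do the same: "A defect, malfunction, or failure of any part of the Medtronic CoreValve™ System", with the delivery and loading systems included. Neither names a surgical valve.

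C.5.1.10 then gives a counting rule, under which every such entry "will be reported on the Adverse Event (AE) eCRF and tabulated as an AE". Harm is not needed, since the rule applies "whether or not associated with any untoward medical occurrence in a subject".

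The general definition in C.5.1.1, repeated in O.2, reads: "An adverse event (AE) is any untoward medical occurrence, unintended disease or injury, or untoward clinical signs". Its first note extends it to both arms: "This definition includes events related to the investigational medical device or the comparator".

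C.5.1.9 defines a device deficiency for medical devices in general and includes malfunctions. C.5.2.4 sends both categories to one form: "Device Deficiencies and Technical Observations should be reported on an Adverse Event eCRF". The same section then describes a class of deficiencies that produced no adverse event but might have led to a serious device effect. It does not say that deficiencies are to be counted as AEs.

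**The concern.** The rule in C.5.1.10 decides what is counted as well as which form is filled in, and the introduction to C.5.1 says that these definitions serve the later analysis as well as data collection. A loading-system fault noticed and dealt with before anything reaches the patient would be counted as that subject's adverse event. It is not a medical occurrence, disease, injury or clinical sign.

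The category belongs to one arm. A summary of all AEs built on this rule would combine patient harm (both arms) with harm-free equipment faults (TAVI only), and any resulting shift could only go against TAVI. The trial is open-label and is meant to support regulatory applications for this device, so a reader of its AE summaries should be able to tell the two apart.

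**Working it through.** The plan states no figure here, so there is nothing to reproduce. The main check is textual.

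**1. Does the rule fit the AE definition?** C.5.1.1 requires a medical occurrence, disease, injury or clinical sign. C.5.1.10 waives that requirement expressly. The two give different answers for a harm-free fault.

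**2. Does it fit C.5.2.4?** Malfunctions are device deficiencies under C.5.1.9, and C.5.2.4 allows for deficiencies with no AE. A transcatheter-valve malfunction of that kind has no AE under C.5.2.4 but is tabulated as one under C.5.1.10.

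**3. Is there a surgical counterpart?** In part. A surgical-valve malfunction can be a device deficiency and can reach the AE eCRF. No instruction has it tabulated as an AE if it did no harm. Prompting also differs. The immediate post-procedure list for TAVI (C.4.7.1) names technical observations among the items to document, whereas the SAVR list (C.4.7.2) asks only for an adverse event review. After 24 months, C.5.2 narrows reporting to listed categories, which still include device-related technical observations.

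**4. Which planned analyses are touched?** The primary endpoint is death or disabling stroke (C.6.5). MACCE (C.5.1.3) and MAE (C.5.1.4) are lists of named events, and a technical observation is not a component of either. None of the labeling objectives in C.6.10.1 is an all-AE rate. No between-arm test of all AEs appears in the text available.

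**5. How large could the effect be?** The documents give neither the rate of harm-free observations nor the overall AE incidence, so the following is illustration only.

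- Subjects per arm: 1600 mITT subjects at 1:1 (C.6.5.2), so 1600/2 = 800.
- q, the share of TAVI subjects with at least one harm-free observation: assumed 0% to 10%.
- p, the true share of subjects with any AE, equal in both arms and independent of q: assumed 30% to 95%.
- m, the mean number of true AEs per subject: assumed 1 to 5, with one harm-free entry per affected subject.

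Extra TAVI entries = 800q. At q = 1% this is 8, and at q = 10% it is 80.

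Excess in TAVI any-AE incidence = [p + (1 − p)q] − p = (1 − p)q.

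- p = 95%, q = 1%: 0.05 × 0.01 = 0.0005, or 0.05 percentage points.
- p = 90%, q = 5%: 0.10 × 0.05 = 0.005, or 0.5 points.
- p = 30%, q = 10%: 0.70 × 0.10 = 0.07, or 7.0 points.

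Ratio of AE counts, TAVI to SAVR = (m + q)/m = 1 + q/m.

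- m = 5, q = 1%: 1 + 0.01/5 = 1.002.
- m = 1, q = 10%: 1 + 0.10/1 = 1.10.

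At q = 0 the excess is 0 and the ratio is 1. With harm-free observations listed separately, the excess is 0 and the ratio is 1.00 for every q.

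**The case against.** A reader might infer that the trial's AE comparison, or an AE table in the labeling, is already biased against TAVI. The documents do not support that. They specify no between-arm all-AE test and no labeling AE table, and the comparisons they do specify use named endpoints. C.6.5.2 leaves further analysis detail to the SAP, and no AE table specification appears in the text available. Technical observations might be shown on a line of their own. This part of the objection stands.

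A reader might also infer that equipment faults can be recorded in one arm only. That goes too far as well, because the device-deficiency route is open to a surgical valve. What remains is an asymmetry in the counting rule, together with uneven prompting.

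Nor do the documents show that true harm rates would be lost. C.5.2 names technical observations alongside adverse events and requires each event to be documented separately, so separating them afterwards looks feasible.

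C.5.1.10 could also be read as a deliberate convention, a specific rule that openly extends a general one. That is a fair reading, but it does not resolve the conflict with C.5.2.4, and a deliberate convention would still mix two kinds of entry in one arm. Showing the observations separately in the SAP would limit the damage, but would sit awkwardly with the protocol sentence, which would still need correcting.

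Finally, any distortion works against the investigational device, so it cannot create a falsely favourable safety result. That lowers the importance of the point without making the tabulation sound.

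**Conclusion.** The point holds in a limited form. C.5.1.10 conflicts with C.5.1.1 and C.5.2.4, and any all-AE count or incidence by arm that follows it would be inflated for TAVI only, to the extent that harm-free observations occur. The direction follows from the text. The size does not: under the assumed ranges, with q from 1% to 10%, the excess in any-AE incidence runs from 0.05 to 7.0 percentage points, and it is nil if there are no such observations. The upper end needs both a low AE incidence (30%) and a high share of affected TAVI subjects (10%). Sample size, power, type I error and the endpoints named above do not depend on this rule. The sentence should be corrected because the conflict is explicit and the remedy cheap; bias in a planned comparison has not been shown.

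**What to change.** Keep the eCRF entry and every reporting duty in C.5.2, including immediate reporting under C.5.2.4. Replace the counting rule in C.5.1.10 with wording such as: *Technical observations are recorded on the AE eCRF and summarised in a table of their own. One contributes to the adverse event tables only if an untoward medical occurrence accompanied it, and in that case the occurrence is the adverse event counted.*

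Flag each technical observation, including those already entered, by whether such an occurrence took place, so that the AE tables can leave out the harm-free ones. State the same rule wherever the AE tables are specified.

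The cost is one sentence and a programming flag. No new data are needed, and device faults become easier to see on their own line.

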### *C.5.2 Reporting*

Investigators are required to keep records on “all relevant observations, including records concerning adverse device effects (whether anticipated or unanticipated)” [21 CFR 812.140; ISO 14155 (2011)]. Adverse event collection will begin from the point of trial enrollment to trial closure. All new or worsening (from baseline) adverse events and technical observations will be captured on the AE eCRF through the 24-month follow-up visit. It is the responsibility of the Investigator to assess the subject for adverse events and capture the required adverse event information on the AE eCRF.

Once a subject has completed their 24-month scheduled follow-up visit only serious adverse events, major adverse events, cardiovascular events, device-related adverse events, including device related technical observations, unanticipated adverse device effects (UADE) or unanticipated serious adverse device effects (USADE), all strokes (CVAs) and deaths will be required to be reported. Reference section C.5.1 Adverse Events for event definitions and criteria. Medtronic representatives or their designees will conduct monitoring visits to review source documentation and verify the complete and accurate capturing of adverse events.

The Investigator must also notify the responsible IRB/MEC regarding new and significant safety information and any event identified by Medtronic that requires expedited FDA, and/or local regulatory agency, reporting as serious, unexpected, and related to the investigational device. It is the responsibility of the investigator to ensure site specific IRB/MEC safety reporting requirements are met.

Medtronic Clinical will ensure all device-related adverse events and all procedure-related SAEs are processed according to internal policies and procedures. When necessary, Medtronic Field Assurance will respond to sites in writing with the findings related to the product experiences.

The general procedure for investigators reporting any adverse event is as follows:

- Report the event to Medtronic as soon as possible but no later than the timeframes outlined below. (At the time of Site Initiation, sites will be provided with the telephone and other applicable contact information of the appropriate Medtronic designee).
- Complete all sections of the Adverse Event eCRF.
- Each unique event/diagnosis must be documented separately.
- Documented pre-existing conditions are not considered to be reportable AEs unless there is a change in the nature or severity of the condition.
- The Adverse Event eCRF must be reviewed by the Investigator.

Reporting guidelines related to specific types of adverse events are outlined below.

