## C.4 Trial Procedures

### C.4.1 Screening Procedures

Prior to any trial-specific tests or procedures, written informed consent must be obtained from the subject. Failure to obtain a signed and hand dated informed consent prior to the procedure constitutes a protocol violation, which is reportable to the IRB/MEC, the Food and Drug Administration (FDA), and other regulatory authorities as applicable.

All potential subjects for trial entry must be screened for eligibility. All patients with symptomatic severe AS that provide informed consent will be entered into the Electronic Data Capture (EDC) system and total number of patients screened will be counted. The reasons why a patient did not enter the Heart Team meeting will be collected (eg. patient does not meet inclusion criteria or meets an exclusion criteria) and, age, STS score, and available screening data.

Data readily available in the patient's medical record may be utilized to fulfill screening requirements and do not need to be repeated. If not previously completed, the following tests and procedures must be performed prior to randomization to verify eligibility. The recommended timeframe for these tests and procedures is within 30 days prior to submission to the Heart Team, unless otherwise specified.

- Demographics and Medical History
- Clinical Assessments – Refer to **Appendix R.19**
  - 5-Meter Gait Speed
  - Grip Strength
- Physical Examination including:
  - Vital signs, weight, height, and body surface area (BSA);
    - BSA will be calculated from height and weight by use of the formula by Dubois and Dubois ( $BSA = 0.007184 \times \text{weight [kg]}^{0.425} \times \text{height [m]}^{0.725}$ )
  - Major systems findings
- NYHA Classification
- Risk Assessments:
  - STS Risk Score – Dataset Version 2.73
  - Logistic EuroSCORE
  - EuroSCORE II
  - SYNTAX Score
  - Katz Index of Independence in Activities of Daily Living
- Co-morbidities
- Routine Laboratory Tests:
  - Complete Blood Count:
    - White Blood Count
    - Hematocrit
    - Hemoglobin
    - Platelet Count
  - Creatinine and Creatinine Clearance
  - Cardiac Enzymes (CK/CK-MB)
  - International Normalized Ratio (INR), if applicable
  - Activated Partial Thromboplastin Time (aPTT)
  - B-type Natriuretic Peptide (BNP) or NT-proBNP
  - Liver Panel:
    - ALT
    - AST
    - Albumin
  - Sodium
  - Potassium

- Transthoracic Echocardiogram (TTE)

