  - Selective coronary arteriography to assess the presence and severity of coronary artery disease which should include angiograms of both coronary arteries and all bypass grafts (if applicable). If the coronary arteriogram has been performed within the last 365 days and the subject qualifies for the trial (no significant coronary artery disease), a more recent exam is not required. However, if the subject had evidence of significant coronary artery disease and/or received a coronary intervention, the exam must be repeated after the intervention and within 90 days of review by the Heart Team.
- 12-lead Electrocardiogram (ECG)

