### C.4.5 Enrollment and Randomization

Prior to randomization and enrollment of a subject, the following must occur:

- Confirm patient signed informed consent
- Confirm patient meets all of the inclusion and none of the exclusion criteria, including approval by the Heart Team

Subjects will be considered enrolled into the trial at the time of randomization (i.e. time of treatment assignment). Randomization will occur only if the patient meets all inclusion criteria and does not meet any exclusion criteria and has been assessed by the Heart Team as being an appropriate candidate for randomization in the SURTAVI trial.

Due to the inclusion/exclusion criteria, not all patients that consent to the trial will be enrolled. All sites will be required to maintain a record of patients screened for the trial meeting general inclusion criteria who have signed the approved informed consent document. For subjects that do not meet trial criteria, the reason for not continuing in the trial must be documented and recorded in the EDC system. Patients consented but not randomized will be considered screen failures and no further trial-related follow-up will be required.

Subjects must have their TAVI or SAVR procedure no later than 30 days post-randomization.

Trial randomization will not be blinded. Once randomization is complete and a treatment arm is assigned, crossover from SAVR to TAVI treatment is not permitted. The sponsor will strictly monitor device dispensation to ensure that only those subjects randomized to the TAVI treatment arm receive the Medtronic CoreValve™ TAV.

Distribution of the subjects within the trial groups will be controlled at the implanting sites by means of central randomization using interactive voice/web randomization service (IXRS). The randomization scheme will be securely stored at the IXRS provider.

---

 Based on protocol design, the time of enrollment will be the same as randomization which is a deviation from ISO 14155 (2011).

Randomization with an assignment to the treatment arm or control arm (TAVI or SAVR) will be executed in a 1:1 ratio. Stratified randomization by investigational site and by the need for coronary revascularization will be used to ensure subjects will be allocated to each comparison group proportionately. Additionally, a blocked randomization scheme with random block sizes will be used within each stratum.

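### Adverse event collection starts at randomization, so serious complications of protocol-required screening CT or coronary arteriography done after consent have no specified reporting route

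*Combined protocol and SAP*

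**What the plan says.** C.5.2 (Reporting) sets the window: "Adverse event collection will begin from the point of trial enrollment to trial closure". C.4.5 fixes the start of that window: "Subjects will be considered enrolled into the trial at the time of randomization", which it explains as the moment the treatment is assigned. A footnote there acknowledges that this departs from ISO 14155 (2011).

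C.4.1 (Screening Procedures) puts consent first: "Prior to any trial-specific tests or procedures, written informed consent must be obtained from the subject". It then states: "If not previously completed, the following tests and procedures must be performed prior to randomization to verify eligibility". The list includes a contrast CT angiogram and "Selective coronary arteriography to assess the presence and severity of coronary artery disease". Reuse is allowed: "Data readily available in the patient's medical record may be utilized to fulfill screening requirements and do not need to be repeated".

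C.5.2 captures events that are new or worse than at baseline, and adds that "Documented pre-existing conditions are not considered to be reportable AEs unless there is a change in the nature or severity of the condition". C.4.5 treats consented patients who are not randomized as screen failures. The reason goes into the EDC system, and nothing more is asked of the site.

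**The concern.** The screening tests are not risk-free. One is an invasive arterial procedure, and the other uses iodinated contrast and radiation. Where no recent examination can be reused, a patient undergoes them because the protocol needs them to establish eligibility. A stroke, vascular injury or contrast-related kidney injury from such a test would be harm arising from trial participation.

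Under C.5.4 the DSMB is to review, at a minimum, all serious adverse events and deaths. An event that is never recorded as an SAE does not enter that review by default, and carries no causality assessment or outcome. What is at stake is how completely the trial accounts for harm from its own procedures.

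**Working it through.** No arithmetic applies. The check is to put the steps in time order and see which rule governs each one.

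1. **Consent.** C.4.1 requires it before any test specific to the trial.
2. **Screening tests.** If not already available, the CT angiogram and arteriogram must be done before randomization (C.4.1). Reuse has limits. A CT from the last 365 days is accepted unless a peripheral intervention has followed it. An arteriogram from the last 365 days is accepted if it showed no significant coronary disease. After significant disease or a coronary intervention, the arteriogram must be repeated within 90 days of Heart Team review. Some patients will therefore be tested after consent.
3. **Heart Team and Screening Committee review** (C.4.2, C.4.3).
4. **Randomization.** This is enrollment (C.4.5), and hence the start of adverse event collection (C.5.2).
5. **Baseline.** The Adverse Events row of Table 3 has its first mark here, after the randomization column. It has none under Screening. The window in C.5.2 is therefore not a stray sentence, because the schedule agrees with it. By contrast, Appendix R.23 collects radiation exposure data at Screening.

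Now take a serious complication arising at step 2 and follow the possible outcomes.

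- **The patient is randomized and the event has resolved or is stable.** It began before the window and is not new or worse from baseline, so C.5.2 does not call for it.
- **The patient is randomized and the event then worsens.** It is reportable under C.5.2.
- **The patient becomes ineligible.** C.3.6.2 excludes patients with a stroke or TIA within 6 months of randomization (criterion 10), an acute MI within 30 days before the index procedure (18), or creatinine clearance below 20 cc/min (26). A complication meeting one of these leads to screen failure. The reason is recorded in EDC (C.4.5) and in IXRS, with the patient's disposition if known (Appendix R.10). Neither record is an SAE report.

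C.5.2.1 asks for every SAE within 3 calendar days of the investigator learning of it, and restates no start date. Note 2 in C.5.1.1 includes procedure-related events in the adverse event definition. Read alone, these would cover step 2. Read under C.5.2 and Table 3, they do not. The text does not say which reading governs, so sites could reasonably differ.

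**The case against.** The best defense is that the enrollment definition was chosen knowingly, as the ISO 14155 footnote shows, and that other routes exist. C.5.2.1 is worded without a time limit. C.5.2 obliges investigators to pass new and significant safety information to their IRB or MEC and to meet local reporting rules. The DSMB may ask for any data it wants. Exposure is also limited: existing records can be reused, and Appendix R.23 notes that screening imaging may predate consent. The case report forms, DSMB charter and Monitoring Plan are not reproduced here and might deal with screening events.

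Much of this stands, and it rules out several stronger readings that a reader might infer:

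- **That such events are never reported, or that oversight bodies cannot see them.** The undated SAE rule, the IRB/MEC duties, the screen-failure records and the reporting of later worsening all contradict this. Radiation skin findings from the Baseline check onward can also be reported (Appendix R.23).
- **That these events count as pre-existing conditions.** No section classifies them so. It is an inference from C.5.2, and for screen failures no classification is made at all.
- **That roll-in subjects have no start of collection.** C.4.4 calls them enrolled and assigned to TAVI, and C.4.5 equates enrollment with treatment assignment. The start is implied, so stating it is only a wording clarification.

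The defense does not close the gap. The footnote discloses the definition without addressing its effect on safety reporting, and a screen-failure reason is no substitute for an SAE record.

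**Conclusion.** The point holds in a limited form. Followed as written, C.5.2, C.4.5 and Table 3 specify no adverse event or SAE collection between consent and randomization. That interval can contain an invasive arteriogram and a contrast CT done only to verify eligibility. C.5.2.1 leaves the position ambiguous.

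The size cannot be calculated. The documents give neither the share of patients tested after consent nor a complication rate. Only patients whose tests follow consent are affected.

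A reader might also infer bias in the trial's result. The documents do not support that: the interval precedes randomization and C.6.1 counts follow-up from the procedure date, so the primary comparison, type I error, power and sample size are unchanged. This is an inexpensive improvement to safety oversight. The verdict assumes that no case report form or charter already supplies the missing rule.

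**What to change.** In C.5.2, state that serious adverse events related to a protocol-required screening procedure are collected and reported from informed consent onward, including in patients who later fail screening. Keep randomization (treatment assignment) as the start for all other events.

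Align three places with this: the screen-failure paragraph in C.4.5, the Adverse Events row of Table 3 under Screening, and the SAE rule in C.5.2.1. While editing, say in C.4.4 or C.5.2 that collection for roll-in subjects starts at assignment to TAVI.

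The cost is a few sentences, a small number of extra SAE reports, and an eCRF change so that the adverse event form can be opened for a patient who has only a Screening ID. No endpoint, threshold or sample size changes.
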